#### 6.6.2. Laboratory Data

All hematology and chemistry laboratory assessments were performed by a central laboratory. Laboratory data will be converted into SI for the analysis. The protocol-specified clinical laboratory (Table 2) findings will be summarized using descriptive statistics by treatment group, without any imputation.

Descriptive statistics will be presented for baseline, each evaluation post baseline, and change from baseline for each post baseline evaluation through 28 days after last dose date.

Laboratory abnormalities will be graded via the Common Terminology Criteria for Adverse Event (CTCAE) or protocol defined severity classification. Laboratory abnormality shifts from baseline will be summarized by treatment group and by reporting periods.

To assess liver injury, a listing of the participants potentially meeting Hy's Law criteria and E-DISH plots will be produced.

## 6.6.3. Vital Signs

Vital signs (body temperature, heart rate, and systolic/diastolic blood pressure) will be summarized using descriptive statistics for baseline and change from baseline for each post-baseline evaluation through 28 days after the last dose date.

#### 7. INTERIM ANALYSES

No interim analysis is planned for this study.

# APPENDICES

# Appendix 1. Summary of Efficacy Analyses

Endpoint	Analysis Type	Population	Data Inclusion and Rules for Handling Intercurrent Events and Missing Data	Main Analysis Model
Primary				
The status of participants achieving resolution of the target ulcer(s) by Week 12	Exact CMH test Descriptive summary statistics Subgroup analysis	ITT	Participants who are lost to follow-up or otherwise drop out of the study without confirmation of resolution of all target study ulcer(s) prior to Week 12, will be classified as non- responder.	Exact CMH test with stratification factors of target ulcer size and duration
Secondary				
Time (in days) to resolution of target ulcer(s) up to Week 12	Log-rank and Cox regression model  Descriptive summary statistics  Subgroup analysis	ITT	For participants who do not have the last target ulcer confirmed resolved by Week 12 or who are discontinued from study, the time to resolution will be censored	Kaplan-Meier method (product-limit estimates) and estimated survival curves will be displayed graphically when appropriate. Graphs will describe the number of participants at risk over time. A stratified log-rank test with stratification factors will be performed to test for differences between the voxelotor and placebo treatment groups
Change from baseline in total surface area of target ulcer(s) at Week 12	LS means (95%CI) LS means difference Descriptive summary statistics Subgroup analysis	ITT	NA	MMRM analysis will be used as described in Section 5.2.2.1 with the stratification factors including target ulcer size (categorical) and target ulcer duration (categorical) as covariates and. The p-value for LS means difference (voxelotor vs. placebo) at Week 12 will be provided.

Endpoint	Analysis Type	Population	Data Inclusion and Rules for Handling Intercurrent Events and Missing Data	Main Analysis Model
Incidence of new ulcers by Week 12	Exact CMH test Descriptive summary statistics Subgroup analysis (age group and country)	ITT	NA	Exact CMH test with stratification factors of target ulcer size and duration
Exploratory				
The proportion of participants achieving resolution of the target ulcer(s) by Week 24	Descriptive summary statistics	ITT	NA	Descriptive statistics
Time (in days) to resolution of target ulcer(s) up to Week 24	Descriptive summary statistics	ITT	NA	Descriptive statistics
Change from Baseline in total surface area of target ulcer(s) over time up to Week 24	Descriptive summary statistics	ITT	NA	Descriptive statistics
Correlation between change in Hb and target ulcer(s) healing at Week 12 and Week 24	Point biserial correlation	ITT	NA	The point biserial correlation $r_{pb}$
Correlation between change in hemolytic parameters (% reticulocytes, indirect bilirubin, LDH) and target ulcer(s) healing at Week 12 and Week 24	Point biserial correlation	ITT	NA	The point biserial correlation $r_{pb}$

Endpoint	Analysis Type	Population	Data Inclusion and Rules for Handling Intercurrent Events and Missing Data	Main Analysis Model
Change from baseline in PRO HRQOL measures: PROMIS-37 v2.0 Pediatric Profile/PROMIS- 43 v2.1 at Week 12 and Week 24	LS means (95%CI) LS means difference Descriptive summary statistics	ITT	NA	Descriptive statistics MMRM analysis will be used as described in Section 5.2.2.1 with the stratification factors including target ulcer size (categorical) and target ulcer duration (categorical) as covariates.
Change from baseline in pain level linked to target ulcer(s) assessed by VAS at Week 12 and Week 24	LS means (95%CI) LS means difference Descriptive summary statistics	ITT	NA	Descriptive statistics MMRM analysis will be used as described in Section 5.2.2.1 the stratification factors including target ulcer size (categorical) and target ulcer duration (categorical) as covariates.
Patient Global Impression of Change (PGI-C) score at Week 12 and Week 24	Descriptive summary statistics	ПТ	NA	Descriptive statistics
Clinician Global Impression of Change (CGI-C) score at Week 12 and Week 24	Descriptive summary statistics	ITT	NA	Descriptive statistics

# Appendix 2. Data Derivation Details

# Appendix 2.1. Definition and Use of Visit Windows in Reporting

Nominal analysis visit windows for the efficacy and safety endpoints will be defined below.

Nominal Visit Time	Target Study Day	Protocol Study Day Range	Study Day Range for Statistical Analysis
Day 1	1	[1, 1]	[1, 1]*
Week 2	14	[11, 17]	[2, 21]
Week 4	28	[25, 31]	[22, 35]
Week 6	42	[39, 45]	[36, 49]

Week 8	56	[53, 59]	[50, 63]
Week 10	70	[57, 63]	[64, 77]
Week 12	84	[81, 87]	[78, 91]
Week 14	98	[95, 101]	[92, 105]
Week 16	112	[109, 115]	[106, 119]
Week 18	126	[123, 129]	[120, 133]
Week 20	140	[137, 143]	[134, 147]
Week 22	154	[151, 157]	[148, 161]
Week 24	168	[165, 171]	[162, 175]
Week 28	196	[191, 201]	[176, 216]

\*: For the leg ulcer Day 1 assessment, the windowing Day 1 visit is defined as [-1,1]

Nominal analysis visit windows for the laboratory assessments will be defined below.

Nominal Visit Time	Target Study Day	Protocol Study Day Range	Study Day Range for Statistical Analysis
Day 1	1	[1, 1]	[1, 1]
Week 12	84	[81, 87]	[2, 125]
Week 24	168	[165, 171]	[126, 216]

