## Follow-up Period (4 weeks after last dose [± 7-day window for EOS Visit])

[figure not shown]
Following completion of the Open-label Treatment Period, eligible participants will be given the option to continue to receive voxelotor (under this protocol, until access is provided through an alternative source). Participants who do not continue to receive voxelotor from an alternative source will be followed for 4 weeks after the last dose of treatment and instructed to return to the site to complete the EOS visit.

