## 3.3.2.2. Early Discontinuation of Study Treatment

Participants may be discontinued from study treatment for any of the following reasons:

- Participant is lost to follow-up
- Adverse event(s)
- Repeated surgical debridement of target ulcer(s) needed to address wound deterioration
- Discretion of the Investigator
- Discretion of the Sponsor
- Pregnancy

The participant should return to the study site for an EOS/Early Termination visit approximately 28 days (±7 days) after the last dose of study treatment, as indicated in the SOA.

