## 6.10. Laboratory Assessments

All laboratory assessments will be performed through a central laboratory. Hematology and serum chemistry will be collected at the Screening visit, Baseline (Day 1), Week 12, Week 24, and EOS/Early Termination. Serum pregnancy test will be performed at the Screening visit, and a urine pregnancy test will be performed at Baseline (Day 1), Week 6, Week 12, Week 18, and Week 24 in female participants who have experienced menarche (see Section 6.10.3 for more information on pregnancy testing). For participants who continue to receive voxelotor beyond 12 weeks in the Open-label Treatment Period (see Section 5.1), hematology and serum chemistry assessments will be conducted every 12 weeks, and urine pregnancy testing will be conducted every 24 weeks. Refer to the SOA (Appendix 1) for the additional details of laboratory tests.

It is the responsibility of the Investigator or designee to assess the clinical significance of all abnormal clinical laboratory values, as defined by the applicable list of normal values on file (ie, local or central laboratory).

For the purpose of this study, a clinically significant laboratory value will be any abnormal result that, in the judgment of the Investigator, is an unexpected or unexplained laboratory value or if medical intervention or corrective action (transfusion, hydration, initiation of antibiotics, or other concomitant medication) is required. Any abnormal values that persist should be followed at the discretion of the Investigator. All clinically significant laboratory value abnormalities are to be recorded as AEs.

Additional and repeat laboratory safety testing for the evaluation of abnormal results and/or AEs during the study may be performed at the discretion of the Investigator or upon request of the Sponsor; it is preferred for the analyses to be conducted by the central laboratory unless medical need necessitates urgent results reporting. Repeat laboratory testing of abnormal potentially clinically significant or clinically significant results for the screening evaluation of the participant may be repeated at the discretion of the Investigator.

Blood specimens collected at the Day 1 visit and Week 12 visit and found to be inadequate for laboratory testing should be redrawn and submitted for laboratory testing within 7 days of the study visit.

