## Appendix 1. Schedule of Assessments

Period	Screening	Run-in	12-Week	12-Week Randomized Treatment			label Treat mum 12 w	Follow- up/ EOS Visit a, v	Early Termination Visit	
Visit Number (Week)	Visit 1 (Week -6 to - 2)	Visit 2 (Week -2)	Visit 3 (Week 0)	Visits 4-8 b (Week 2-10)	Visit 9 (Week 12)	Visits 10-14 c (Week 14- 22)	Visit 15 (Week 24)	Visit 16-A & onward d (Week 28)	Visit 16-B (Week 28)	
Visit Day	-42 to -14	-14	Day 1	Day 14-70	Day 84	Day 96-154	Day 168	Day 196 & onward	Day 196	
Visit Window	_	+3 days	+ 1 day	±3 days	±3 days	±3 days	±3 days	±5 days	±7 days	_
Informed consent/assent	Х									
HbSS, HbS/β  thalassemia test e	Х									
Inclusion/exclusionf	X	X	Xg							
Medical history	X									
Height and weight	X				Xh					
Physical examination i	X	X	X		X		X	$\mathbf{X}^{j}$	X	X
Vital signs k	X	X	X	X	X	X	X	$\mathbf{X}^{l}$	X	X
Serum pregnancy test m	X									
Urine pregnancy test n			X	X	X	X	X	X°		
Hematology p	X		X		X		X	$\mathbf{X}^{l}$	X	X
Serum chemistry q	X		X		X		X	X 	X	X
PROMIS-43 v2.1 PROMIS-37 v2.0 Pediatric Profile r			X		X		X			
VAS r			Xg		X		X			
PGI-C r					X		X			
CGI-C					X		X			

Period	Screening	Run-in	12-Week	12-Week Randomized Treatment			label Treat num 12 wo	Follow- up/ EOS Visit a,v	Early Termination Visit	
Visit Number (Week)	Visit 1 (Week -6 to - 2)	Visit 2 (Week -2)	Visit 3 (Week 0)	Visits 4-8 b (Week 2-10)	Visit 9 (Week 12)	Visit 10-14 c (Week 14- 22)	Visit 15 (Week 24)	Visit 16-A & onward d (Week 28)	Visit 16-B (Week 28)	
Visit Day	-42 to -14	-14	Day 1	Day 14-70	Day 84	Day 96-154	Day 168	Day 196 & onward	Day 196	
Visit Window	_	+3 days	+1 day	±3 days	±3 days	±3 days	±3 days	±5 days	±7 days	_
Target ulcer(s) assessment s	х	X	Xg	X	X	Х	Х		X	X
SOC	X	X	X	X	X	X	X	X 	X	X
Randomization			X							
Dispense study drugt			X	X	Xu	X		X 		
Collect study drug				X	X	X	X	X 	Xw	X
Dispense dosing diary			X		X					
Collect dosing diary				X	X	X	X		Xw	X
Concomitant medications	X	X	X	X	X	X	X	X 	X	X
Adverse events	X	X	X	X	X	X	X	$\mathbf{X}^{l}$	X	X

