Abbreviations: ALT, alanine aminotransferase; AST, aspartate aminotransferase; BUN, blood urea nitrogen; CGI-C, Clinician Global Impression of Change; EOS, End of study; Hb, hemoglobin; HbS/β0, sickle hemoglobin and one beta thalassemia gene; HbSS, sickle hemoglobin with 2 sickle cell genes; LDH, lactate dehydrogenase; MCH, mean cell hemoglobin; MCHC, mean corpuscular hemoglobin concentration; MCV, mean corpuscular volume; PGI-C, Patient Global Impression of Change; PROMIS, Patient-Reported Outcome Measurements Information System; RBC, red blood cell; RDW, red blood cell distribution width; SOC, standard of care; VAS, visual analog scale; WBC, white blood cell.

- a. Week 28 (Visit 16-B) will be for participants who choose not to enroll or are ineligible for the provision of voxelotor through an alternative source study. At this visit, safety and efficacy assessments will be collected.
- Visits at Weeks 2, 4, 6, 8, and 10.
- Visits at Weeks 14, 16, 18, 20, and 22.
- d. For participants who have completed 12 weeks in the Open-label Treatment Period and continue to receive voxelotor until they have access to voxelotor from an alternative source (eg, through a clinical OLE study sponsored by Pfizer, commercialization of the product, or a managed access program; See Section 5.1). The final study visit for these participants will occur on the day of access to voxelotor from an alternative source.

Period	Screening	Run-in	12-Week Randomized Treatment				label Treat num 12 wo	Follow- up/ EOS Visit a,v	Early Termination Visit	
Visit Number (Week)	Visit 1 (Week -6 to - 2)	Visit 2 (Week -2)	Visit 3 (Week 0)	Visits 4-8 b (Week 2-10)	Visit 9 (Week 12)	Visit 10-14° (Week 14- 22)	Visit 15 (Week 24)	Visit 16-A & onward d (Week 28)	Visit 16-B (Week 28)	
Visit Day	-42 to -14	-14	Day 1	Day 14-70	Day 84	Day 96-154	Day 168	Day 196 & onward	Day 196	
Visit Window	_	+3 days	+1 day	±3 days	±3 days	±3 days	±3 days	±5 days	±7 days	_

- e. This test will be performed at Screening only for the medical diagnosis of SCD, if this diagnosis is not documented in the participant's medical chart.
- f. All Screening evaluations must be completed and reviewed before the Run-in Visit to confirm all eligibility criteria are met. Inclusion and exclusion criteria should be reviewed at Screening, Run-in, and just prior to randomizing each participant to ensure study eligibility is met.

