Visit Number (Week)	Visit 1 (Week -6 to - 2)	Visit 2 (Week -2)	Visit 3 (Week 0)	Visits 4-8 b (Week 2-10)	Visit 9 (Week 12)	Visit 10-14° (Week 14- 22)	Visit 15 (Week 24)	Visit 16-A & onward d (Week 28)	Visit 16-B (Week 28)	
Visit Day	-42 to -14	-14	Day 1	Day 14-70	Day 84	Day 96-154	Day 168	Day 196 & onward	Day 196	
Visit Window	_	+3 days	+1 day	±3 days	±3 days	±3 days	±3 days	±5 days	±7 days	_

- t. Study drug will be dispensed at the Day 1, Week 6, Week 12, and Week 18 visits. For participants who continue to receive voxelotor beyond 12 weeks in the Open-label Treatment Period (See Section 5.1), study drug will be dispensed every 12 weeks.
- Participants demonstrating initial ulcer-re-epithelization at Week 12 will continue treatment in their assigned treatment group for an additional 2 weeks to confirm ulcer resolution.
- v. Participants transitioning to a program providing voxelotor through an alternative source will complete assessments on the day they transition to that program. Study drug for this study should not be taken on the day of that visit (dose will be taken on that day as part of the alternative source program).
- w. Only required for participants transitioning to a program providing voxelotor through an alternative source

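### If the SAP's laboratory windows are applied as written, scheduled EOS draws (Days 189-203) are labelled Week 24, although the general table in the same appendix puts those days in Week 28

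*SAP*

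**What the plan says.** **Windows.** SAP Appendix 2.1 has two tables. The general one, for efficacy and safety endpoints, gives Week 24 the analysis range Days 162-175 and Week 28 the range Days 176-216. A second table follows: "Nominal analysis visit windows for the laboratory assessments will be defined below". It has three rows (Day 1, Week 12, Week 24), and its Week 24 row has target Day 168, protocol range Days 165-171 and analysis range Days 126-216. There is no Week 28 or EOS row.

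**Draws.** Protocol 6.10 schedules laboratory samples at both visits: "Hematology and serum chemistry will be collected at the Screening visit, Baseline (Day 1), Week 12, Week 24, and EOS/Early Termination". In the Schedule of Assessments (Protocol Appendix 1), the EOS visit is Visit 16-B at Day 196 ± 7 days, with hematology and chemistry marked. Its note a begins "Week 28 (Visit 16-B) will be for participants who choose not to enroll". Participants who do not continue voxelotor "will be followed for 4 weeks after the last dose of treatment". Those who stop early return for an "EOS/Early Termination visit approximately 28 days (±7 days) after the last dose of study treatment" (Protocol 3.3.2.2).

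**Other SAP text.** SAP 2.3.3 defines the study visit as the nominal visit on the CRF and runs the on-treatment period to at most 28 days after the last dose. SAP 6.6.2 limits descriptive laboratory summaries to 28 days after the last dose. SAP 2.3.2 ends the open-label efficacy period at Week 24, but defines the open-label safety extension period to include follow-up.

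**The concern.** The same calendar day carries two visit labels depending on which table is read. Under the laboratory table, a scheduled post-dosing sample shares a label with the Week 24 sample that it was meant to follow.

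The two samples are not obviously interchangeable. The protocol says voxelotor raises Hb and lowers hemolysis measures (1.2 and 1.4). It also withholds Hb, bilirubin and reticulocyte results from investigators during the randomized period because they may suggest the treatment assignment (3.4.1.1). The documents do not say how far these values move in the 4 weeks after stopping, so the size of any distortion cannot be stated.

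Two outputs could be touched. Week 24 by-visit laboratory rows could mix on-drug values with values taken about 4 weeks after the last dose, or rest on the later value alone when the Week 24 draw is missing. The exploratory Week 24 correlations of Hb, % reticulocytes, indirect bilirubin and LDH with healing could also be touched. Neither Appendix 2.1 nor 6.6.2, as supplied, says which value is used when two fall in one window.

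**Working it through.** **Inputs.** Laboratory Week 24 window Days 126-216; general Week 24 window Days 162-175; general Week 28 window Days 176-216 (all SAP Appendix 2.1). Visit 16-B at Day 196 ± 7 (Protocol Appendix 1). EOS/Early Termination at 28 ± 7 days after last dose (Protocol 3.3.2.2). Limit of 28 days after last dose (SAP 6.6.2).

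**1. The plan's own ranges.** 84 ± 3 = Days 81-87 and 168 ± 3 = Days 165-171, as the laboratory table states. Its lower edge for Week 24 is the midpoint (84 + 168)/2 = 126. Its upper edge, 216, is not a midpoint with Week 28, which would be (168 + 196)/2 = 182. It equals the upper edge of the general table's Week 28 window.

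**2. Where scheduled EOS draws fall.** 196 − 7 = 189 and 196 + 7 = 203, which is 15 days. All 15 lie inside Days 126-216 (laboratory Week 24) and inside Days 176-216 (general Week 28). Counting instead from a last dose on Days 165-171 gives 165 + 21 = 186 to 171 + 35 = 206. All 21 of those days fall the same way.

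**3. Extent of the disagreement.** The laboratory Week 24 window is 216 − 126 + 1 = 91 days long. Of these, 216 − 176 + 1 = 41 are Week 28 in the general table.

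**4. What the 28-day limit removes.** With last dose on Day 168, the limit falls on 168 + 28 = Day 196. Days 189-196 (8 of 15) stay in the summary and Days 197-203 (7 of 15) are dropped.

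**5. Early Termination draws.** With last dose on Day L, the draw falls on L + 21 to L + 35. It can reach Days 126-216 when L + 35 ≥ 126 and L + 21 ≤ 216, so L = 91 to 195. With the window cut at Day 175, it can still reach Week 24 for L = 91 to 154 (175 − 21 = 154). Moving the bound alone is therefore not enough. By the same formula, L up to 125 − 21 = 104 can reach the laboratory Week 12 window (Days 2-125).

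**6. Check of the proposed cut.** With Week 24 as Days 126-175 (50 days) and Week 28 as Days 176-216, all 15 EOS days move to Week 28 and all scheduled Week 24 days (165-171) stay in Week 24.

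Separately, the general table's Week 28 protocol range, Days 191-201, is 196 ± 5. That is the Visit 16-A window ("Day 196 & onward", ± 5 days), not the ± 7 of Visit 16-B. This does not affect the analysis windows.

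**The case against.** **The CRF label may govern.** A reader might infer that every EOS draw will in fact be reported as Week 24. The documents do not settle that. SAP 2.3.3 defines the visit by the CRF, and on that reading EOS draws keep their own label. This stands, and it is why the point is conditional. It does not remove the point: Appendix 2.1 sets ranges expressly for statistical analysis, and the SAP does not say which rule prevails.

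**Pooling follow-up safety data is declared.** A reader might infer that the laboratory safety assessment as a whole is compromised. The documents do not support this. SAP 2.3.2 deliberately includes follow-up in the open-label safety extension period, laboratory shifts are summarized by reporting period, and the Hy's Law listing and E-DISH plots have no stated dependence on the Week 24 label. This stands and confines the safety effect to by-visit descriptive rows, which carry no hypothesis test.

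**The correlations may be protected.** They are exploratory efficacy endpoints, and the open-label efficacy period ends at Week 24. SAP 5.2.4 is partly redacted and Appendix 4 is not in the supplied text, so a rule may exist there. This stands: an effect on the correlations is possible, not shown.

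**The wide window may be intended to capture data.** It may be. But the same appendix separates those days for other endpoints, and the protocol schedules two distinct draws, so any intended pooling should be stated.

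**Not every late draw is off drug.** For participants who continue voxelotor, "The final study visit for these participants will occur on the day of access to voxelotor from an alternative source". Those who move to another source "will complete assessments on the day they transition to that program". This also stands: the 4-week gap applies to participants who stop.

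**Conclusion.** The point holds in conditional form and is minor. If the laboratory windows are applied as written, draws on all 15 permitted Visit 16-B days are labelled Week 24, against Week 28 in the general table. The 28-day limit removes only those more than 28 days after the last dose; the 8-to-7 split assumes a last dose on Day 168.

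The reach is Week 24 by-visit descriptive laboratory summaries and possibly the exploratory Week 24 correlations. Primary and secondary endpoints do not depend on this label. All counts above are calendar days, not samples. SAP section 2 records a dosing pause in May 2024 and termination in September 2024, so early stopping is a real setting here, but the documents do not say how many draws are affected.

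**What to change.** In SAP Appendix 2.1:

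1. End the laboratory Week 24 window at Day 175 and add a Week 28 row for Days 176-216, matching the general table.
2. Show draws recorded on the CRF as EOS (Visit 16-B) or Early Termination in a separate follow-up row, whatever their study day. State which CRF label a transition-day draw carries, because such a draw is not a post-dosing sample.
3. Assign all other draws by window. If several fall in one window, use the value nearest the target day. Other conventions exist; what matters is that one is written down.

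The on-treatment definition (SAP 2.3.3), the 28-day limit (6.6.2) and the open-label safety extension period (2.3.2) stay unchanged.

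The cost is one bound, two rows and a short selection rule. Some participants, number unknown, may have no Week 24 laboratory value. Step 2 also takes Early Termination draws out of the Week 12 window, with the same possible consequence there. The Week 28 row may hold few scheduled draws: continuing participants are sampled every 12 weeks, which counted from Week 24 gives 168 + 84 = Day 252.
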